## **6.2 Dosage, Preparation and Administration of Study Products**

### **6.2.1 Dose and Regimen**

As outlined in [Section 4.2](#), each subject will receive injections with MRG-201 and placebo around the site of two separate 6-mm punch biopsies. The treatment for each wound site will be

randomized (left versus right) and blinded but consistent throughout dosing. MRG-201 and placebo will each be administered as four 20- $\mu$ L injections around one wound site, with subjects receiving approximately 5.3 mg of MRG-201 active moiety on each dosing day (approximately 1.3 mg per 20- $\mu$ L injection).

Study treatment injections for subjects receiving 6 doses in their initial treatment cycle will be administered on Days 1, 3, 5, 8, 10, and 12 of the first cycle of study dosing. A second cycle of 6 study treatment injections will be administered for subjects who exhibit evidence of keloid formation (defined as meeting a score of 1 or 2 on the mVSS and having an appearance consistent with an area likely to form a keloid according to investigator judgement) within 12 weeks after initiation of the first cycle of study dosing and following the initial 29-day treatment and assessment period. The treatment regimen for the second cycle of study dosing will be the same as for the first cycle, i.e., an initial dose on Day 1 followed by additional doses on Days 3, 5, 8, 10, and 12, with follow-up visits at Days 19 and 29 after the re-start of dosing.

Subjects in additional optional cohorts may receive blinded study treatment injections on Days 1, 3, 5, 8, 10, 12, 15, 17, 19, 22, 24, and 26 and will not be given a second cycle of dosing.

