## **7.2 Safety Assessments**

### **7.2.1 Adverse Events**

AEs will be assessed at each study visit by direct observation and subject interviews. The severity of AEs will be evaluated using the NCI CTCAE, version 5.0. All AEs that occur from initiation of study treatment through 30 days after the last dose of study treatment must be recorded, regardless of causal assessment to study treatment.

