#### **8.4.10 Days 57, 113, 141, 197, 225, 281, 309, 337 ( $\pm$ 7 Days)**

- Obtain vital signs (blood pressure, heart rate, respiratory rate, and body temperature).
- Perform physician assessment of keloid formation and volume.

- Assign mVSS and POSAS scoring ([Fearmonti et al 2010](#), see [Appendix D](#) and [Appendix E](#)).
- Review and record AEs and concomitant medications.
- Note: Biopsy wound sites are to be photographed at the time the investigator suspects a keloid may be forming, at the time of observation of an unconfirmed keloid, and at the time of keloid confirmation.

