## 9.4 Collection and Reporting of Adverse Events

### 9.4.1 Initial Reporting of Adverse Events

Subjects will be evaluated and questioned generally to identify adverse events during the course of the study. Any events occurring prior to administration of the first dose of study treatment will be recorded on the Medical History eCRF. Events occurring after administration of the first dose of study treatment or those that increase in severity or frequency will be recorded as treatment-emergent AEs on the Adverse Event eCRF. Adverse events that occur up to and including 30 days after administration of the last dose of study treatment must be reported.

All AEs spontaneously reported by the participant and/or in response to an open question from study personnel or revealed by observation, physical examination, or other diagnostic procedures will be recorded on the Adverse Event eCRF. Any clinically relevant deterioration in laboratory assessments or other clinical findings, as assessed by the Investigator, is considered an AE and

must be recorded on the Adverse Event eCRF. In addition, an abnormal test finding will be classified as an adverse event if one or more of the following criteria are met:

- The test finding is accompanied by clinically significant symptoms.
- The test finding necessitates additional diagnostic evaluation(s) or medical/surgical intervention; including additional concomitant drug treatment or other therapy. Note: simply repeating a test finding, in the absence of any of the other listed criteria, does not constitute an AE.
- The test finding leads to a change in study treatment dosing or discontinuation of subject participation in the clinical research study.
- The test finding is considered an AE by the Investigator.

Wherever possible, a specific disease or syndrome rather than individual associated signs and symptoms should be identified. However, if an observed or reported sign or symptom is not associated with a documented disease or syndrome, the sign or symptom should be recorded as a separate AE. Laboratory data are to be collected as stipulated in this protocol. Clinical syndromes associated with laboratory abnormalities are to be recorded as appropriate (e.g., diabetes mellitus rather than hyperglycemia).

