### **11.4.3 Analysis of the Safety Endpoint: Safety and Tolerability**

#### ***11.4.3.1 Adverse Events***

The analysis of the safety endpoint will be based on AE incidence, physical examination findings, vital signs, ECG results and changes in clinical laboratory tests.

Adverse events will be coded by preferred term and system organ class using the Medical Dictionary for Regulatory Activities (MedDRA®) and summary tables for all AEs will be

generated for the FAS. Incidence rates and percentages will be summarized for each preferred term and system organ class. Additional summary tables will be generated for the following subsets: subjects with SAEs, subjects with related AEs, subjects with severe (Grade 3 or 4) AEs, and subjects who discontinue due to AEs. Depending on the doses achieved in this study, AEs may also be summarized by dose level. Severity, investigator-attributed relationship to study treatment, and action taken will also be recorded.

Concomitant medications will be coded using the World Health Organization Drug Dictionary (WHO-DD; 01 September 2017 or later version). A dictionary listing of all unique concomitant medications used in the study will be provided.

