Abbreviations: AE = adverse event; aPTT = activated partial thromboplastin time; ECG = electrocardiogram; eCRF = electronic case report form; FSH = follicle-stimulating hormone; HIV = human immunodeficiency virus; INR = international normalized ratio; PK = pharmacokinetic(s); PT = prothrombin time; SAE = serious adverse event

- a) Day 1 refers to the first dosing day for the first double-blind active treatment period.
- b) Complete physical examination at screening and Day 1; brief physical examination at all other time points.
- c) Only for women who are not surgically sterile as confirmation of menopause.
- d) Serum pregnancy test at screening and urine pregnancy tests on Days 1, 12, 29, 85 and at the end of the study for female subjects.
- e) Performed at screening, predose on Day 1, on Day 2 (approximately 24 hours after Day 1 dosing), and predose on Day 12.
- f) Hematology, clinical chemistry, and urinalysis (including microscopy) will be collected predose as indicated in the protocol. Laboratory assessments do not need to be performed on Day 1 if screening laboratory measurements were performed within 3 days prior to Day 1.
- g) 6-mm punch biopsy to create two excisional wounds (one treated with MRG-201 and one treated with placebo on Day 1) as described in the Study Manual.
- h) Subjects will receive intradermal injections of MRG-201 and intradermal injections of placebo at each time point. Refer to the Study Manual for detailed instructions on intradermal injections – Biopsy Site Selection, Injection, and Brief Photography Instructions.
- i) All AEs, including SAEs, will be recorded from the time of administration of the first dose of study treatment on Day 1 until 30 days after the last dose of study treatment or the end of study visit, whichever occurs last. Treatment-related AEs ongoing at the follow-up visit should be followed to resolution or until the investigator considers them “chronic” or “stable.”
- j) All medications (including over-the-counter medicines, herbal treatments, supplements, and vitamins) administered 30 days before the first administration of study treatment (Day 1) until the end of study (Day 365) will be recorded on the eCRF.
- k) On Day 1 and Day 12, plasma for PK will be drawn at 1 hour ( $\pm$  10 minutes), 2 hours ( $\pm$  15 minutes), and 3 hours ( $\pm$  15 minutes) after injection.
- l) On Day 2 and Day 13, plasma for PK will be drawn 24 ( $\pm$  4) hours after Day 1/12 dosing.

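### The protocol contradicts itself on how long AEs are collected, and its AE tables have no time split, so events near dosing may be pooled with about 10 months of later follow-up

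*Combined protocol and SAP*

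**What the plan says.** - **Label.** Section 9.4.1 says that events "occurring after administration of the first dose of study treatment or those that increase in severity or frequency will be recorded as treatment-emergent AEs". The label starts at the first dose and has no end. No treatment-emergent window is defined elsewhere in the supplied text.
- **Shorter period.** The next sentence of 9.4.1 reads: "Adverse events that occur up to and including 30 days after administration of the last dose of study treatment must be reported". Section 7.2.1 agrees: "All AEs that occur from initiation of study treatment through 30 days after the last dose of study treatment must be recorded". Section 9.5.1 uses the same limit for SAE reports.
- **Longer period.** Footnote i of Appendices A, B and C has all AEs, SAEs included, recorded from the first dose "until 30 days after the last dose of study treatment or the end of study visit, whichever occurs last". The visit lists match it: "Review and record AEs and concomitant medications" appears at the four-weekly visits (for example Section 8.4.10) and again at the end-of-study visit in Section 8.5.
- **Tables.** Section 11.4.3.1 plans tables of all AEs on the Full Analysis Set: "Incidence rates and percentages will be summarized for each preferred term and system organ class". It adds subsets for SAEs, related AEs, Grade 3 or 4 AEs and discontinuations due to AEs, and an optional summary by dose level. It names no time window.
- **Dosing.** In Section 6.2.1 the 6-dose cycle is "administered on Days 1, 3, 5, 8, 10, and 12 of the first cycle of study dosing", and the 12-dose schedule is "Days 1, 3, 5, 8, 10, 12, 15, 17, 19, 22, 24, and 26". Subjects on 6 doses may have a second 6-dose cycle.
- **Comparator.** Every subject receives both MRG-201 and placebo (Section 6.2.2).

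**The concern.** Safety is the first-listed objective, and the AE tables are its main output. Two things are unsettled at once: how long AEs are collected, and which part of that period a table covers.

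The first is a matter of data quality. A site that takes 7.2.1 and 9.4.1 as a limit would stop recording about six weeks into a 6-dose course. A site that follows footnote i would record for a year. With about four sites and cohorts of 12 to 16, AE counts could then differ by site for reasons that have nothing to do with the drug.

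The second is a matter of reading the results. No group receives placebo only, so systemic AEs have no concurrent untreated comparator. Onset relative to dosing is one of the few internal signals available, and a single whole-study table does not show it. The optional summary by dose level does not replace it. Section 2.2 allows the longer schedule at 5.3 mg, so grouping by dose level alone would not separate 6 doses from 12.

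**Working it through.** **1. The plan's own duration.** Screening of up to 28 days plus 365 days gives 28 + 365 = 393 days, which reproduces the maximum participation in the synopsis. Nominal follow-up from Day 1 is therefore taken as 365 days.

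**2. Length of the 30-day window.** Window end = last dose day + 30. For a second cycle starting on Day S, the last dose falls on Day S + 11 (Section 4.2) and the window ends on Day S + 41. Section 8.3 places S after the first 29-day period and within 12 weeks, so nominally Day 29 to Day 85.

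| Course | Last dose | Last window ends | Days inside windows | Days outside | Share outside |
|---|---|---|---|---|---|
| 6 doses, one cycle | Day 12 | Day 42 | 42 | 323 | 88.5% |
| 12 doses | Day 26 | Day 56 | 56 | 309 | 84.7% |
| 6 + 6, restart Day 29 | Day 40 | Day 70 | 70 (windows overlap) | 295 | 80.8% |
| 6 + 6, restart Day 57 | Day 68 | Day 98 | 42 + 42 = 84 | 281 | 77.0% |
| 6 + 6, restart Day 85 | Day 96 | Day 126 | 42 + 42 = 84 | 281 | 77.0% |

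For single-cycle subjects the time outside is 323/30.44 = 10.6 months or 309/30.44 = 10.2 months.

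**3. What each reading puts in the tables.** If footnote i governs, all the time outside is pooled with the window. If 7.2.1 and 9.4.1 govern, almost none of it is; Section 9.6 would still bring in late events thought to be caused by the product. The treatment-emergent label does not decide this, because 11.4.3.1 counts all AEs. The recording period and the absent table window decide it.

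**4. How much pooling could matter.** The documents give no background AE rate, so this is an illustration. Assume a constant background rate λ per subject-month and a drug-caused risk d = 20%, all falling inside the 42-day window, compared with a dose level that has no effect. Then P(AE by day t) = 1 − (1 − d)·exp(−λt/30.44), and the risk difference is d·exp(−λt/30.44). From Day 42 to Day 365 the difference shrinks by the factor exp(−λ × 323/30.44).

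| λ per month | Difference, Day 42 | Difference, Day 365 | Factor | Ratio, Day 42 | Ratio, Day 365 |
|---|---|---|---|---|---|
| 0.005 | 19.9% | 18.8% | 0.948 | 29.9 | 4.2 |
| 0.02 | 19.5% | 15.7% | 0.809 | 8.2 | 1.7 |
| 0.05 | 18.7% | 11.0% | 0.588 | 3.8 | 1.24 |
| 0.10 | 17.4% | 6.0% | 0.346 | 2.35 | 1.09 |

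A rare term keeps almost all of its difference. A frequent term, or the any-AE row, loses most of it. In a cohort of 12 with λ = 0.10, the gap is 12 × 0.174 = 2.1 subjects at Day 42 and 12 × 0.060 = 0.7 subjects at Day 365.

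**5. Are the two periods alike apart from drug?** No. In Appendix A, AEs are reviewed at 10 visits up to Day 29 (Days 1, 2, 3, 5, 8, 10, 12, 13, 19, 29) and at 12 visits from Day 57 to Day 365. That is one visit per 42/10 = 4.2 days inside the window and one per 323/12 = 26.9 days after it. In Appendix C there are 16 visits by Day 36. The early period also holds the biopsies, the suturing and the placebo injections.

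**The case against.** A reader might infer more than the documents support, and the case against those readings is good.

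- **That collection to Day 365 is settled.** It is not. Two sections set the 30-day limit, one of them in the sentence directly after the label. If they govern, the pooling largely disappears. What stands is the contradiction itself.
- **That the open-ended label causes the pooling.** The sentence mainly tells sites whether an event belongs on the Medical History form or the Adverse Event form. Since 11.4.3.1 does not tabulate treatment-emergent events as such, redefining the label alone would change no table.
- **That whole-year tables dilute any drug effect.** Step 4 shows otherwise for rare terms. Most drug-related events in Phase 1 were injection-site erythema or edema (Section 2.1.3.2), which should have little late background. The related-AE table also separates some background, and per-patient listings keep timing visible in cohorts this small. The related-AE table rests on investigator judgement, though, and Section 9.3.1 asks that no other cause explain the event, so a common complaint can be set aside case by case.
- **That an on/off rate comparison would isolate the drug.** Step 5 shows that it would not: AEs are sought far more often early, and the procedures fall there too.

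It is also fair to say that Section 11.1 promises a separate SAP, written before any data are reviewed, and that a table window is usual SAP content. That document is not in the supplied text, so its silence cannot be assumed. The contradiction on collection, however, sits in the protocol that sites follow. Finally, Section 11.2 disclaims formal hypotheses, so what is at stake is clear description, not a test.

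**Conclusion.** The point holds in a limited form. The AE collection period is contradictory as written, and the AE tables have no time window. If footnote i governs, 85% to 88% of a single-cycle subject's follow-up is pooled with the dosing window; after a second cycle the last window ends at about Day 70 to Day 126, depending on when that cycle starts. For terms with appreciable background incidence this can mask clustering around dosing or a difference between regimens. For rare terms and for events with little late background the effect is small.

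The day counts rest only on the schedule. The attenuation figures rest on assumed background rates of 0.005 to 0.10 per subject-month and an assumed 20% drug-caused risk, neither of which is in the documents. The broader conclusion that the tables would dilute every drug effect is not supported. This is a cheap improvement to the reporting of the first-listed objective, together with a contradiction that needs to be resolved.

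**What to change.** 1. Reconcile Sections 7.2.1, 9.4.1 and 9.5.1 with footnote i of Appendices A to C and with the visit lists, so that all sites capture AEs and SAEs over the same stated period.
2. In Section 11.4.3.1 (or the SAP) keep the whole-study tables of all AEs, SAEs and related AEs. Add a split by onset: first dose through 30 days after the last dose of each cycle, with overlapping windows merged, against all later time. Give subject-time for each period. Apply the same window to the treatment-emergent label in 9.4.1.
3. State that the comparison of periods is descriptive, because visit frequency and the biopsy and injection procedures also differ between them.

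If the shorter collection period is the one intended, the split is largely redundant and item 1 is the main change.

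The cost is a few sentences and a second set of AE tables built from onset dates already collected, with no new visits or procedures. The drawback is more tables to read; late-onset events stay visible because the whole-study tables are kept.

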#### **9.4.2 Follow-up of Adverse Events**

All AEs considered to be related to study treatment will be followed until resolution or stabilization.

### **9.5 Collection and Reporting of Serious Adverse Events**

#### **9.5.1 Initial Serious Adverse Event Reports**

All SAEs that occur up to and including 30 days after administration of the last dose of study treatment must be reported by the Investigator to the Sponsor or Sponsor's designee within 24 hours of awareness of the event by submission of a SAE Notification Form. Investigators must report to the Sponsor any SAE, whether or not considered drug related, including those listed in the protocol or Investigator's Brochure. The initial report must contain at a minimum a subject identifier code, an event term, and an assessment of causality. The SAE Notification Form should be e-mailed to:

If the Investigator is unable to complete and send the SAE Notification Form within the timeframe required, the SAE must be reported via phone call to:

Primary Contact

Back-up Contacts

An Investigator may be requested by the Sponsor to obtain specific follow-up information in an expedited fashion. This information may be more detailed than that captured on the Adverse Event eCRF. In general, this will include a description of the SAE in sufficient detail to allow for a complete medical assessment of the case and independent determination of possible causality. Information on other possible causes of the event, such as concomitant medications and illnesses must be provided. In the case of a subject death, a summary of available autopsy findings must be submitted as soon as possible to the Sponsor or the Sponsor's designated representative.

### **9.5.2 Follow-up of Serious Adverse Events**

All SAEs should be followed up until resolution or stabilization. The timelines and procedure for follow-up reports are the same as those for the initial report.

New information regarding an SAE that becomes available after the submission of the initial SAE Notification Form must be reported by the Investigator to the Sponsor by completion of a SAE Follow-up Report Form or through other written documentation (e.g., laboratory tests,

discharge summary, postmortem results). Follow-up reports and/or written documentation must be provided to the Sponsor within 24 hours of the Investigator's receipt of the information.

## **9.6 Post-Trial Adverse Events**

Any AE that occurs outside of the protocol-specified observation period or after the end of the trial but is considered to be caused by the investigational product must be reported to the Sponsor.

## **9.7 Pregnancy Reporting and Follow-up**

Pregnancy in a female clinical trial participant is not an SAE per se. Complications of such pregnancies, for example, spontaneous abortion, may qualify as an SAE and should be reported as an SAE even if they occur after the SAE reporting period has ended.

The Investigator must notify the Sponsor via telephone or e-mail within 24 hours of awareness of a pregnancy in a study participant and must complete the Pregnancy Notification Form and submit it to the Sponsor within 2 working days of being notified. The participant will not receive any further doses of their assigned study treatment. The pregnancy must be followed to determine outcome, including spontaneous or voluntary termination, details of birth, and the presence or absence of any birth defects, congenital abnormalities, or maternal and/or newborn complications. This follow-up should occur even if the intended duration of safety follow-up for the trial has ended. Information regarding the course of the pregnancy, including perinatal and postnatal offspring outcome up to 8 weeks of age should be reported as follow-up information on the Pregnancy Notification Form. While treatment will be discontinued for pregnant subjects, study observations may continue to evaluate study endpoints.

Male study participants will be instructed to notify the Investigator if a female partner becomes pregnant during the study. The Investigator must notify the Sponsor within 24 hours via telephone or e-mail and must complete the Pregnancy Notification Form and submit it to the Sponsor within 2 working days of being notified. The Investigator should obtain informed consent from the subject's partner allowing the Investigator to obtain information regarding the pregnancy and its outcome. If the subject's partner provides informed consent, the Investigator should follow the pregnancy until outcome as described above for female study participants and report the follow-up information on the Pregnancy Notification Form.

## **9.8 Halting Rules**

Safety data will be reviewed on an ongoing basis by the Sponsor's Medical Monitor. While no formal stopping rules will be implemented, the Sponsor may suspend enrollment or terminate the study at any time for safety concerns.

## **9.9 Emergency Sponsor Contact**

In a medical emergency (i.e., an event that requires immediate attention regarding operation of the clinical study and/or the use of investigational drug), study site staff will apply appropriate medical intervention according to current standards of care, and contact the Medical Monitor or the designated Sponsor representative, as indicated in [Section 1](#) of this protocol.

# **10 TRIAL-SPECIFIC COMMITTEES**

No study-specific committees will be used for this trial.

